13 PUBLICATION PLAN

All publication rights are delineated in the Clinical Study Agreement and/or other separate agreements with the Investigator and/or Institution, as applicable.

14 CONFLICT OF INTEREST POLICY

14.1 Finance, Insurance, and Indemnity

Arrangements for finance, insurance, and indemnity are delineated in the Clinical Study Agreement and/or other separate agreements with the Investigator and/or Institution, as applicable.

16 APPENDICES

Appendix A New York Heart Association Class Guidelines

The NYHA heart failure functional classifications are provided below.

NYHA Class I (mild): Patients with cardiac disease but without resulting in limitation of physical activity. Ordinary physical activity does not cause undue fatigue, palpitation (rapid or pounding heart beat), dyspnea (shortness of breath), or anginal pain (chest pain).

NYHA Class II (mild): Patients with cardiac disease resulting in slight limitation of physical activity. They are comfortable at rest. Ordinary physical activity results in fatigue, palpitation, dyspnea, or anginal pain.

NYHA Class III (moderate): Patients with cardiac disease resulting in marked limitation of physical activity. They are comfortable at rest. Less than ordinary activity causes fatigue, palpitation, dyspnea, or anginal pain.

NYHA Class IV (severe): Patients with cardiac disease resulting in the inability to carry on any physical activity without discomfort. Symptoms of heart failure or the anginal syndrome may be present even at rest. If any physical activity is undertaken, discomfort is increased.

Source: New York Heart Association 1994

Appendix B Prohibited and Restricted Medications

Subjects taking prohibited medications at study entry will not be eligible for the study.

Subjects who require current treatment with a prohibited medication will be withdrawn from the study.

Subjects who have previously taken a prohibited medication during the study will be withdrawn from the study unless:

- the prohibited medication has been discontinued AND
- withdrawal from the study presents an unacceptable medical risk to the subject

The justification to allow the subject to continue in the trial will be made by the Sponsor/Medical Monitor with medical input from the Investigator, and will be documented. If allowed to remain in the trial, this will be reported as a major protocol deviation and not a waiver.

The table below lists prohibitions and restrictions by medication class, including representative medications within class. A **prohibited** medication is not allowed. A **restricted** medication is allowed only under certain conditions.

Medication Class	Medication ^a	Prohibition/restrictions
Analgesics	RESTRICTED 
• acetaminophen	
• Only acetaminophen (not combinations including acetaminophen) is allowed as rescue medication for OA pain in the knee (at a maximum daily dose of 2500 mg)• Subjects are encouraged to limit the amount of rescue medication (i.e., acetaminophen) taken during the study. Subjects must discontinue taking study-provided rescue medication during the Baseline Pain Assessment Period and for at least 24 hours prior to the start of study visits. Rescue medication use during the Baseline Pain Assessment Period through Visit 3 and within 24 hours of the study visits (Visits 5, 6, and 8) will be documented in the EDC.
Anticonvulsants	PROHIBITED 
• gabapentin• pregabalin• carbamazepine	
• Prohibited use within 4 weeks prior to Screening and throughout the study
Antidepressants	PROHIBITED 
• tricyclic antidepressants• duloxetine• monoamine reuptake inhibitors	
• Prohibited use within 4 weeks prior to Screening and throughout the study

Medication Class	Medication ^a	Prohibition/restrictions
	
 • serotonin norepinephrine reuptake inhibitors 	
Anxiolytics	PROHIBITED 
 • chlordiazepoxide • diazepam • flurazepam • alprazolam • clonazepam • lorazepam • oxazepam • temazepam • midazolam • triazolam 	
 • Prohibited at study entry and throughout the study
HMG-CoA reductase inhibitor (Statin)	RESTRICTED	
 • HMG-CoA reductase inhibitors are restricted and cannot be initiated after screening and throughout the study. Subjects who are on a stable dose of a statin at screening may be eligible for enrollment.
Miscellaneous	PROHIBITED 
 • intra-articular injections into the index knee, approved and unapproved (i.e., hyaluronic acid and corticosteroids) • unapproved treatments (e.g., platelet-rich plasma, topical capsaicin, lidocaine, and diclofenac) • cannabidiol (CBD) • COVID-19 vaccine 	
 • Prohibited use within 3 months of Screening and throughout the study • Prohibited throughout the study • Use of CBD is prohibited within 1 month prior to Screening and throughout the study • Subject must not be planning to receive a COVID-19 vaccine during Screening through 30 days of the last dose of study drug. If the subject has received a COVID-19 vaccine, they must be fully vaccinated at least 1 week before the Screening visit and be symptom free
Nonsteroidal anti-inflammatory drugs (NSAIDs)	PROHIBITED 
 • ibuprofen 	
 • Prohibited use following Screening • Prohibited use within 7 days or five half-lives of the drug prior to the Baseline Pain Assessment Period, whichever is longer

Medication Class	Medication ^a	Prohibition/restrictions
	RESTRICTED 
• aspirin	
• Aspirin, at a dose of up to 81 mg per day, is allowed for prophylaxis of coronary and cerebrovascular events if stable for 30 days prior to Screening and the dose is expected to remain the same throughout the duration of the study• Aspirin should not be used with an anticoagulant
Opioids	PROHIBITED 
• methadone• oxycodone• codeine• morphine• hydrocodone• fentanyl	
• Prohibited use following Screening• Prohibited use within 7 days or five half-lives of the drug prior to the Baseline Pain Assessment Period, whichever is longer• Prohibited use of immediate- or extended-release or controlled-release opioids, transdermal fentanyl, or methadone within 3 months of Screening• Use of opioids, for the treatment of pain other than OA of the knee, with a morphine equivalent dose of ≥ 30 mg per day for more than 2 days per week within 1 month prior to Screening
Steroids and immunosuppressant drugs	PROHIBITED 
• oral corticosteroids	
• Prohibited use within 30 days prior to the screening visit• Prohibited throughout the study

^a Medications within each class include but are not limited to the examples listed in this table.

BMI	body mass index
BPI-sf	Brief Pain Inventory - Short Form
COVID-19	Coronavirus disease 2019
C-SSRS	Columbia-Suicide Severity Rating Scale
ECG	electrocardiogram
eCRF	electronic case report form
EOT	end of treatment
ET	early termination
GSD	Guidance for Site Documentation and Data Management Querying of Data Impacted by COVID-19
HADS	Hospital Anxiety and Depression Scale
K-L	Kellgren-Lawrence
MedDRA	Medical Dictionary for Regulatory Activities
msec	milliseconds
NRS	numerical rating scale
OA	osteoarthritis
PCI	potentially clinically important
PGIC	Subject Global Impression of Change
QID	four times daily
QTcB	QT interval corrected for heart rate using Bazett's formula
QTcF	QT interval corrected for heart rate using Fridericia's formula
SAE	serious adverse event
SAP	statistical analysis plan
SAS®	Statistical Analysis System
SD	standard deviation
SE	standard error
SF-12	12-item Short Form Survey
SOC	system organ class
TEAE	treatment-emergent adverse event
TESAE	treatment-emergent serious adverse event
WOMAC	Western Ontario and McMaster Universities Osteoarthritis Index

1 INTRODUCTION

This statistical analysis plan (SAP) provides a technical and detailed elaboration of the statistical analyses of safety and efficacy data as described in the study protocol Amendment 4 dated 16 February 2022. This trial was terminated on 8 August 2022 with 61 patients randomized.

Specifications for tables, figures, and listings are contained in a separate document. Statistical analyses for population pharmacokinetic (PK) and PK/pharmacodynamics (PD) modeling will be presented in a separate report and therefore will not be included in this SAP.

This plan should be read in conjunction with the study protocol and the electronic case report forms (eCRF)

2 OBJECTIVES

2.1 Primary Objective

The primary objective of this study is to evaluate the efficacy of ACP-044 compared with placebo in the treatment of pain associated with osteoarthritis (OA) of the knee.

The primary endpoint is:

The primary endpoint is change from Baseline to Week 4 in the weekly average of the daily average Numeric Rating Scale (NRS) pain intensity scores.

2.2 Secondary Objective

The secondary objective of this study is to evaluate the efficacy of ACP-044 compared with placebo in the treatment of pain associated with osteoarthritis (OA) of the knee.

The key secondary endpoints are:

- Patient Global Impression of Change (PGIC) at Week 4 with reference to baseline status
- Change from Baseline to Week 4 in Western Ontario and McMaster Universities Osteoarthritis Index (WOMAC) total score and individual subscale scores for pain, stiffness, and physical function
- Proportion of subjects who are responders as defined by 30% and 50% reduction from Baseline to Week 4 in the weekly average of the daily average NRS pain intensity scores

Additional secondary endpoints are:

- Change from Baseline to Week 4 in:
 - Weekly average of the daily worst NRS pain intensity scores
 - Brief Pain Inventory–Short Form (BPI-sf)

- 12-item Short Form Survey (SF-12)

2.3 Exploratory Objective

The exploratory objective of this study is to evaluate the use of rescue medication in subjects with pain associated with OA of the knee treated with ACP-044 compared with placebo.

2.4 Safety Objective

The safety objective of this study is to evaluate the safety and tolerability of ACP-044 compared with placebo in the treatment of pain associated with OA of the knee.

2.5 Pharmacokinetic Objective

The PK objective of the study is to characterize the PK profile of ACP-044 in subjects with pain associated with OA of the knee.

2.6 Pharmacokinetic/Pharmacodynamic Objective

The pharmacokinetic/pharmacodynamic (PK/PD) objective of the study is to characterize the exposure-response relationship using appropriate modelling and simulation methods.

3 STUDY DESIGN

3.1 General Study Design

This is a Phase 2, randomized, double-blind, placebo-controlled, parallel-group study to evaluate the efficacy and safety of ACP-044 in subjects with pain associated with radiographically confirmed OA of the knee. The study will compare active treatment groups, receiving either 800 mg ACP-044 BID or 400 mg ACP-044 QID, with a placebo group. The Sponsor, subjects, and Investigators will be blinded to treatment assignment.

The study periods are:

- Screening: up to 4 weeks
- Baseline Pain Assessment: a 7-day period during which open-label placebo will be taken and baseline pain assessments will be recorded. Additional 3-day window may be added, if needed.
- Double-blind treatment: 4 weeks
- Safety follow-up: approximately 7 days after end of treatment (EOT)/early termination (ET) and approximately 30 days after the last dose of study drug

Screening Period (Up to 4 weeks)

During the Screening period, subjects will be assessed for study eligibility. All subjects must have radiographically confirmed OA of the knee, including review of imaging and

confirmation of a Kellgren-Lawrence (K-L) score of 2 or 3. Subjects who have had an X-ray of the index knee within 12 weeks of Screening may provide a historical image for central reading to confirm eligibility, or imaging can be done during Screening at protocol-trained radiological sites. Randomization visits cannot occur until there is confirmation from the central reader that there are no exclusionary findings on the knee joint images. The index knee is defined as the most painful knee at Screening.

Prohibited analgesic medications must be discontinued during the Screening period. Investigators must not withdraw a subject's prohibited medication other than analgesics solely for the purpose of enrolling them into the study. Medications will be discontinued only if it is deemed clinically appropriate to do so and in consultation with the prescribing physician.

All pain medication, except for the study-provided rescue medication (acetaminophen), will be discontinued 7 days or 5 half-lives, whichever is longer, prior to the Baseline Pain Assessment Period. In the event of inadequate pain relief, acetaminophen may be taken with a maximum daily dose of 2500 mg.

Rescreening of a subject will be allowed, with the approval of the Medical Monitor.

Baseline Pain Assessment Period (1 Week)

Following eligibility at screening, subjects will complete a Baseline Pain Assessment Period that will occur approximately 7 days before randomization; an additional 3-day window may be added, if needed. During the Baseline Pain Assessment Period, subjects will be instructed in the use of a handheld device (electronic diary [eDiary]) to record their daily pain scores and rescue medication use. Compliance with recording of pain score and use of rescue medication will be assessed for continued subject eligibility.

Subjects must discontinue taking study-provided rescue medication during the Baseline Pain Assessment Period and for at least 24 hours prior to the start of study visits. Rescue medication use during the Baseline Pain Assessment Period through Visit 3 and within 24 hours of the study visits (Visits 5, 6, and 8) will be documented in the electronic data capture (EDC).

Subjects who enter the Baseline Pain Assessment Period will not be allowed to rescreen. Subjects who experience technical issues with the device and their pain scores were not assessed may be rescreened and the Baseline Pain Assessment Period may be extended, if needed and with permission of the Sponsor.

Treatment Period (4 Weeks)

At Baseline (Week 0), eligible subjects will be randomly assigned in a 1:1:1 ratio to receive ACP-044 800 mg BID, ACP-044 400 mg QID, or placebo, according to a randomization schedule. Randomization will be stratified by sex and baseline K-L score (2 or 3).

All efficacy assessments will be completed and a PK blood sample will be taken at the Baseline visit prior to administration of the first dose of study drug. Subjects will continue daily entry into the eDiary of pain scores, compliance with ingestion of study medication, and rescue medication use from Week 0 through to Week 4/EOT/ET.

Subjects will receive their first dose at the study site after all Baseline assessments have been completed and a PK blood sample will be taken approximately 1 hour after dosing. Dosing is four times a day.

During the treatment period (Week 0 through Week 4), subjects will be permitted to use only acetaminophen as rescue medication. Subjects will record their use of acetaminophen in their eDiary. Subjects must discontinue acetaminophen use for at least 24 hours prior to the start of study visits in order to minimize the confounding effects of the rescue medication on efficacy measurements.

A PK sample will be taken at each study visit according to the schedule described in the Pharmacokinetic Assessments section.

[figure not shown]
At the Week 4 visit, end of treatment (EOT) procedures will be completed.

Safety Follow-up Period (30 Days)

Safety will be further assessed during a follow-up visit to occur in the clinic approximately 7 (± 3) days after EOT/ET procedures. During this in-clinic visit, pain intensity, adverse events (AEs), and concomitant medications will be assessed, since the EOT/ET. Then, a follow-up telephone call will occur approximately 30 (+4) days after the last dose of study drug to assess AEs and concomitant medications.

The study design schematic is presented in [Figure 1](#). The schedule of assessments is provided in [Appendix A](#).

Figure 1 Schematic of Study Design

Abbreviations: BID=twice daily; EOT=end of treatment; QID=four times daily; R=randomization

3.2 Schedule of Assessments

Schedule of events and assessments can be found in [Appendix A](#).

3.3 Randomization

On Day 1 eligible subjects who meet inclusion and do not meet exclusion criteria will be randomized in a 1:1:1 ratio to receive ACP-044 800 mg BID, ACP-044 400 mg QID, or placebo, according to a randomization schedule. Randomization will be stratified by sex and baseline K-L score.

Approximately 50 United States (US) sites will participate in this study.

3.4 Blinding

Treatment assignments will be blinded to all study subjects, Investigators, site personnel, and Sponsor personnel.

In order to maintain the double-blind design of the study, all subjects will receive the same numbers of tablets at the same intervals, regardless of the treatment group to which they are randomized. Placebo tablets will be size- and color-matched to the ACP-044 tablets.

The investigational products are ACP-044 400 mg tablets, or matching placebo (size- and color-matched) tablets. Study drug doses are to be administered orally for 4 weeks.

Doses to be studied are:

- ACP-044 800 mg dose delivered two times a day (provided as 2×400 mg ACP-044 tablets)
- ACP-044 400 mg dose delivered four times a day (provided as 1×400 mg ACP-044 tablet)

- Placebo, size- and color-matched to ACP-044 tablets

Blinded drug will be provided in blister cards. All subjects will take the same number of tablets per day in order to maintain the blinded study design.

Dosing is to occur in the morning (2 tablets), noon (1 tablet), evening (2 tablets), and night (1 tablet) and should occur at the same time each day over the duration of the study.

Table 1 Blinded Daily Dosing Regimen

	First Daily Dose	Second Daily Dose	Third Daily Dose	Fourth Daily Dose
Placebo	PP	P	PP	P
ACP-044 400 mg QID (four times daily)	XP	X	XP	X
ACP-044 800 mg BID (twice daily)	XX	P	XX	P

Abbreviations: P=ACP-044 placebo tablet; X=ACP-044, 400 mg tablet

3.5 Determination of Sample Size

Approximately 240 subjects will be randomized in a 1:1:1 ratio to ACP-044 800 mg BID dose, ACP-044 400 mg QID dose, or placebo. Assuming a treatment difference of 0.85 and a common standard deviation of 1.7 between an ACP-044 dose arm and placebo, 64 subjects per arm is needed to provide approximately 80% power to detect this treatment difference using a 2 sample t-test at 2-sided alpha level of 0.05. Assuming a discontinuation rate of 20%, 80 subjects per treatment group will be randomized.

The planned sample size is 240 subjects randomized (80 subjects per treatment group).

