12.4 Multiple Comparisons / Multiplicity

The primary efficacy endpoint is change from baseline to week 4 in the average of the daily average Numeric Rating Scale (NRS) pain intensity scores. For the primary efficacy analysis, the null hypothesis is that there is no treatment effect between 400 mg QID and placebo during the study versus the alternative hypothesis that there is a treatment effect. Similar hypothesis applies to the comparison of 800 mg BID to placebo.

The overall Type I error is controlled by a hierarchical testing procedure. The procedure is to test the difference of the treatment effect between 400 mg QID versus placebo first, at significant level $\alpha=0.05$. If this test is significant, then comparison for 800 mg BID versus placebo will be performed at $\alpha=0.05$ level.

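### SAP 3.5 still gives 240 subjects and about 80% power after termination at 61 randomised; the achieved power, and the power of the second hierarchical step, are not stated

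*SAP*

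**What the plan says.** SAP section 3.5 repeats the calculation in protocol section 9.3. The inputs are given as "Assuming a treatment difference of 0.85 and a common standard deviation of 1.7 between an ACP-044 dose arm and placebo", and the result is that "64 subjects per arm is needed to provide approximately 80% power to detect this treatment difference using a 2 sample t-test", two-sided at 0.05. It then adds: "Assuming a discontinuation rate of 20%, 80 subjects per treatment group will be randomized". The section calls 240 the planned size but puts randomisation in the future tense.

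Section 1 of the same document states: "This trial was terminated on 8 August 2022 with 61 patients randomized". Appendix B gives 21 September 2022 as the date of version 1.0, so the whole SAP was written after the trial stopped.

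Section 12.4 tests 400 mg QID against placebo first, at 0.05. For the other regimen it says: "If this test is significant, then comparison for 800 mg BID versus placebo will be performed at" the same level.

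Section 19 lists the changes caused by termination. The primary ANCOVA on the Full Analysis Set stays, with baseline observation carried forward (BOCF) for missing data. Key secondary endpoints become descriptive. For the other secondary and the exploratory endpoints inference is expressly withdrawn; no such statement is made for the primary. Sample size, power and the section 12.4 hierarchy are not mentioned.

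**The concern.** The only power figure in the SAP belongs to a trial about four times larger than the one analysed (240/61 = 3.9). It stands beside a primary test that is retained. A reader who takes section 3.5 at face value would give a non-significant primary result more weight against a 0.85-point effect than 61 subjects can support.

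The second issue does not depend on termination. Section 3.5 sizes the trial for one ACP-044 arm against placebo and does not separate the two regimens. Protocol section 9.5.2 left multiplicity to the SAP, and section 12.4 then placed 800 mg BID behind a gate. A gated comparison succeeds only if both tests succeed, so its power is lower than the per-comparison figure. The SAP does not state that cost.

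**Working it through.** **Inputs (SAP 3.5, 1 and 12.4).** Difference 0.85; SD 1.7; two-sided alpha 0.05; two-sample t-test; 64 evaluable and 80 randomised per arm; 1:1:1 allocation; 61 actually randomised; 400 mg QID tested before 800 mg BID.

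**1. The plan's own figure.** Standardised effect = 0.85/1.7 = 0.50. Noncentrality = 0.50 × √(n/2), and power comes from the noncentral t with 2n − 2 df.
- n = 64: noncentrality 0.50 × √32 = 2.83, critical t 1.979, power 80.1%.
- n = 63: power 79.5%, so 64 is the right number.
- Dropout: 64/0.80 = 80 per arm; 3 × 80 = 240.

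The planning figures reproduce.

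**2. Power at 61 randomised.** The documents do not give the split by arm. Assuming near-equal arms, 61/3 = 20.3 per arm: noncentrality 0.50 × √(20.33/2) = 1.59, critical t 2.023, power 34.3%. With 20 v 20 it is 33.8%; with 20 v 21, 34.5%.

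**3. Range at 61.** Neither the Full Analysis Set count nor the amount of missing data is given, so the following are assumptions:

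| Assumption | Power per comparison |
|---|---|
| BOCF sets 20% of each arm to no change: effect 0.80 × 0.85 = 0.68, SD kept at 1.7 | 24% |
| 20% lost and not analysed (16.3 per arm) | 28% |
| All 61 contribute, no covariate gain | 34% |
| Baseline–outcome correlation 0.5: SD 1.7 × √(1 − 0.25) = 1.47 | 43% (44% with the ANCOVA's pooled error df, 61 − 6 = 55) |

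**4. Precision.** The difference detectable with 80% power is 1.55 at 20 per arm (1.53 at 20.3), against 0.85 planned. At 20 per arm the 95% CI half-width is about 2.024 × 1.7 × √(2/20) = 1.09, so an observed difference of exactly 0.85 would not be significant.

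**5. The second hierarchical step.** Power for 800 mg BID is the probability that both tests are significant. The two test statistics share the placebo arm (correlation about 0.5). By simulation with 1,000,000 replicates and both true differences equal to 0.85:
- 64 per arm: 69% (bivariate normal approximation 69.7%).
- 80 per arm, all with complete data: 80.4%.
- 20 per arm: 19%; 21 per arm: 20%.

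Sensitivity at 64 per arm:
- 800 mg BID kept at 0.85 and 400 mg QID at 1.0, 1.2 or 1.5: 76%, 79% and 80%.
- Both at 0.85 with covariate correlation 0.3, 0.4 or 0.5: 74%, 78% and 83%.

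**The case against.** The strongest reply is that nothing in section 3.5 is miscalculated. It explains how the size was chosen, it agrees with the protocol, and it calls 240 planned. All of that stands: a reader might infer an arithmetic error, and there is none.

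Nor is the shortfall hidden. The first paragraph of section 1 gives the termination date and the 61, and section 19 attributes its changes to early termination. A reader might infer that the SAP presents an 80%-powered trial as completed; read as a whole, it does not. What remains is that the power statement was carried forward without a label or an achieved figure, in a section that neither refers to the 61 nor is addressed in section 19.

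On the hierarchy, a reader might infer that the SAP claims 80% for 800 mg BID, or that this comparison could never have had 80%. Neither is supported. The SAP makes no power statement for the second step, and sizing per comparison is common practice. Power near 80% is reachable with complete data from all 80 per arm, a larger 400 mg QID effect, or appreciable covariate gain. The first of these is contrary to the plan's 20% discontinuation: imputation in the Full Analysis Set does not restore lost information. The plan claims neither of the other two.

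A single value of 34% would be false precision, because the arm split, the analysis-set count and the effect of BOCF are unknown. This stands, and it is why a range is needed.

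Finally, power computed after enrolment ends changes no analysis; the confidence interval conveys the precision, and section 5.1 already makes intervals two-sided 95%. That is fair. Wording a non-significant result in advance as inconclusive, or making the interval the main display, would be a reporting preference and is not asked for here.

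**Conclusion.** The point holds as a mismatch between the stated size and power and the trial being analysed. No value in the range of about 24% to 43% per comparison approaches 80%. The central 34%, the 19% for both steps and the detectable 1.55 rest on the planning effect and SD, near-equal arms, all 61 contributing and no covariate gain.

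The hierarchy point is smaller: it is an unstated consequence of section 12.4. The 69% for 800 mg BID applies to 64 evaluable per arm, equal true differences of 0.85 and no covariate gain, and should not be quoted without those conditions.

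No result or analysis changes. The matter affects how the primary result is read, and whether the reader can tell if the hierarchical test is still in force.

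**What to change.** In SAP section 3.5:
- Label the existing text as the original plan and put it in the past tense.
- Add that 61 were randomised. Under the planning assumptions this gives about 34% power per comparison (about 24% to 43% across stated assumptions on BOCF and covariate gain), about 19% for both hierarchical steps, and a detectable difference of about 1.55. Update these once the arm split and Full Analysis Set count are known.
- Note that the planned 80% was per comparison. Give the 800 mg BID figure of about 69% at 64 evaluable per arm, with its assumptions.

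In SAP section 19, state whether the section 12.4 hierarchy remains in force for the truncated trial, and report the estimates with the 95% intervals already specified in section 5.1.

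The cost is SAP wording only, with no change to data, design or conduct. The stated figures become less favourable.
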